### 3.1.3. Change in vital signs

Vital signs include systolic and diastolic blood pressure (mmHg), heart rate (beats per minute), respiratory rate (breaths per minute) and body temperature.

Change will be described using change from baseline. Rules for defining baseline are described in Appendix 1.2.

## 3.2. Secondary Endpoint(s)

### 3.2.1. Annualized rate of VOC

A VOC (Vaso-Occlusive Crisis) is defined as an acute episode of pain that:

- Has no medically determined cause other than a vaso-occlusive event, and
- Results in a visit to a medical facility (hospitalization, emergency department, urgent care center, outpatient clinic, or infusion center), and
- Requires parenteral narcotic agents, parenteral nonsteroidal anti-inflammatory drugs (NSAIDs), or an increase in treatment with oral narcotics.

VOC are categorized as:

- **Uncomplicated VOC:** a VOC that is NOT classified as an Acute Chest Syndrome (ACS), hepatic sequestration, splenic sequestration, priapism, or dactylitis.
- **Complicated VOCs:** includes ACS, hepatic sequestration, splenic sequestration, priapism, or dactylitis.

The annualized rate of VOC will be calculated as specified in Section 6.2.1.

### 3.2.2. Change from baseline in hematological laboratory parameters, including hemoglobin, reticulocytes, lactate dehydrogenase, and unconjugated bilirubin.

Hemoglobin will be reported in g/dL units.

Reticulocytes will be reported in 10^9/L units.  
Lactate dehydrogenase will be reported in IU/L units.  
Unconjugated bilirubin will be reported in umol/L units.

Rules for defining baseline are described in Appendix 1.2.

### 3.2.3. Incidence of SCD-related AEs

SCD-related AEs are defined as AEs with any of the Preferred Terms listed below:

- Sickle Cell Anemia with crisis
- Acute chest syndrome
- Hepatic sequestration
- Splenic sequestration
- Priapism
- Dactylitis
- Pneumonia
- Osteonecrosis
- Stroke
- Leg Ulcers

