#### **9.4.12. Disease-related Events or Disease-related Outcomes Not Qualifying as AEs or SAEs**

##### **9.4.12.1. Adverse Events that are Vaso-Occlusive Crisis Events**

VOC events are not reported as an AE/SAE and must be reported on the VOC page.

If the underlying cause of an SAE is determined to be a VOC, then the SAE will be entered on the VOC page and not reported as an SAE.

If the underlying cause of an SAE is determined not to be a VOC, then the SAE must be recorded in the SAE page and reported as an SAE.

The following disease-related events are common in participants with SCD, independent of exposure to study intervention, can be serious/life-threatening, and are defined as endpoints in this protocol:

- Uncomplicated VOC (defined as an acute episode of pain with no medically determined cause other than a vaso-occlusive event, results in a visit to a medical facility (hospitalization, emergency department, urgent care center, outpatient clinic, or infusion center), and requires parenteral narcotic agents, parenteral nonsteroidal anti-inflammatory drugs (NSAIDs), or an increase in treatment with oral narcotics, but is NOT classified as an acute chest syndrome, hepatic sequestration, splenic sequestration, dactylitis, or priapism.)
- Complicated VOC:
  - Acute chest syndrome
  - Hepatic sequestration
  - Splenic sequestration
  - Priapism requiring a visit to a medical facility
  - Dactylitis

Because these events are typically associated with the disease under study, they will not be reported according to the standard process for expedited reporting of SAEs even though the event may meet the definition of an SAE. These events will be recorded on the VOC page in the participant's CRF within 72 hours. These disease-related events will be monitored by an independent data monitoring committee and safety review team on a routine basis.

Note: However, if either of the following conditions applies, then the event must be recorded and reported as an SAE (instead of disease-related events):

- The event is, in the investigator's opinion, of greater intensity, frequency, or duration than expected for the individual participant.

OR

- The investigator considers that there is a reasonable possibility that the event was related to study intervention.

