#### **9.4.12.1.1. Procedures for Reporting and Documenting VOC Event Data**

All VOCs, as defined in Section 9.4.12.1, are to be documented within the eCRF within 5 days of a site becoming aware of such event. Each VOC is to be recorded only once on the "Vaso-Occlusive Event" eCRF page. All VOCs are to be recorded throughout the entire treatment period, up to Week 48, and should continue until the Follow-Up Visit at Week 60 for participants who do not enroll in the OLE study (or earlier if participant discontinues from the study). The Investigator will classify and provide all the following information for each VOC as follows:

- Diagnosis, which will be limited to one of the pre-defined VOC events as described in Section 9.4.12.1:
  - Uncomplicated VOCs
  - Acute chest syndrome
  - Hepatic sequestration
  - Splenic sequestration
  - Priapism (requiring a visit to a medical facility)
  - Dactylitis
- Onset date,
- Stop date,
- Action taken (none, required concomitant medication, temporarily withheld study drug, permanent discontinuation of study drug, or other [explain]),
- Whether or not hospitalization or a visit to emergency department, urgent care center, outpatient clinic, or infusion center was required,
- Concomitant medications given, and
- Outcome (recovered without sequelae, resolved with sequelae, ongoing, unknown, death).

If a participant is hospitalized due to a VOC and during hospitalization develops a non-VOC event that meets the criteria for a SAE, then that event should be reported as a SAE. Any prolongation of a hospitalization due to a non-VOC event (even though they may have initially been hospitalized due to a VOC) is reportable as a SAE in the eCRF.

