### 2.1. Modifications to the Analysis Plan Described in the Protocol

- All VOC data will be summarized including the events that occur after the inter-current events described in the protocol.
- All data for hemoglobin, reticulocytes, lactate dehydrogenase, and unconjugated bilirubin will be summarized including the data after the inter-current events described in the protocol.
- Updated definition of PK analysis set.
- Changed endpoint from “Incidence of SCD-related SAEs” to “Incidence of SCD-related AEs” to include all AEs.

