#### 6.1.1. Incidence of TEAEs

AEs will be mapped to system organ class (SOC) and preferred term using the Medical Dictionary for Regulatory Activities (MedDRA).

The following guidelines will be used to capture the different types of TEAEs based on the AE CRF:

- **Treatment-Related Adverse Events:** adverse events with relationship to study treatment (as recorded on the AE eCRF page, Relationship with study treatment = Related) reported by the investigator and those of unknown relationship (i.e., no answer to the question 'Relationship with study treatment').
- **Serious Adverse Events (SAE):** serious adverse events (as recorded on the AE eCRF page, Was the AE Serious = Yes).
- **Non-Serious Adverse Events:** non-serious adverse events (as recorded on the AE eCRF page, Was the AE Serious = No).
- **Adverse Events Leading to Interruption of Study Treatment:** adverse events leading to interruption of study treatment (as recorded on the AE eCRF page, Action taken with study treatment = Drug interrupted).
- **Adverse Events Leading to Dose Reduction:** adverse events leading to dose reduction (as recorded on the AE eCRF page, Action taken with study treatment = Dose Reduced).
- **Adverse Events Leading to Discontinuation of Study Treatment:** adverse events leading to discontinuation of study treatment (as recorded on the AE eCRF page, Action taken with study treatment = Drug Permanently Discontinued).
- **Adverse Events Leading to Death:** adverse event leading to death (as recorded on the AE eCRF page, Did the AE result in Death = Yes, as well as AEs of Grade 5).

TEAEs leading to study discontinuation will be derived based on the response to the following question in the AE CRF form: "Caused Study Discontinuation"

The overall incidence of TEAEs will be summarized (Section 5.3). This table includes: TEAEs (number of TEAEs and participants with TEAEs),

Number of participants with:

- TEAEs by maximum severity,
- Treatment-related TEAE,
- Treatment-related TEAE by maximum severity,
- Treatment emergent SAE,
- Treatment-related treatment emergent SAE,
- Treatment emergent non-serious AE,
- TEAEs leading to study discontinuation,
- TEAEs leading to study treatment discontinuation,

TEAEs leading to study treatment interruption,  
TEAEs leading to dose reduction,  
TEAEs leading to death.

The TEAEs will be summarized and tabulated at participant level using counts and percentages:

- TEAEs by SOC and PT
- TEAEs by SOC, PT and maximum reported severity

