### 6.2.3. Incidence of SCD-related AEs

Treatment-emergent SCD-related AEs will be summarized as follows (additional details in Section 6.1.1).

- Treatment emergent SCD-related AEs by SOC and PT
- Treatment-related treatment emergent SCD-related AEs by SOC and PT
- Treatment emergent SCD-related Serious AEs by SOC and PT
- Treatment-related treatment emergent SCD-related Serious AEs by SOC and PT

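### The SCD-related AE endpoint is tabulated from the AE page, but the protocol by default records six of its ten terms on the VOC page, so incidence is understated and selectively captured

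*SAP*

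**What the plan says.** SAP 3.2.3 defines the endpoint by a list of ten terms: "SCD-related AEs are defined as AEs with any of the Preferred Terms listed below". SAP 6.2.3 then specifies four tables: all events, treatment-related events, serious events, and treatment-related serious events. It refers back for the rules: "Treatment-emergent SCD-related AEs will be summarized as follows (additional details in Section 6.1.1". Those rules rest on one form: "The following guidelines will be used to capture the different types of TEAEs based on the AE CRF". The protocol's endpoint was SCD-related SAEs. SAP 2.1 widens it to AEs "to include all AEs", with no mention of the VOC page.

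The protocol separates VOCs from AEs. Section 9.4.12.1 states: "VOC events are not reported as an AE/SAE and must be reported on the VOC page". Where a VOC underlies an SAE, "the SAE will be entered on the VOC page and not reported as an SAE". Section 9.4.12.1.1 limits the VOC-page diagnosis to six choices: uncomplicated VOC, acute chest syndrome, hepatic sequestration, splenic sequestration, priapism needing a facility visit, and dactylitis.

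There are exceptions. Under 9.4.12.1, an event goes to SAE reporting if the investigator judges it beyond what is expected for that participant, or possibly related to study drug. Under 9.4.12.1.2, an SAE that the adjudication committee rejects as an endpoint returns to the site for SAE reporting.

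**The concern.** An endpoint named for SCD-related events draws on a form from which the most characteristic SCD events are, by default, kept out. A reader of the 6.2.3 tables would take the acute chest syndrome or crisis rows as the incidence of those complications. They would in fact show only the cases that left the usual recording route. Because the exceptions select on severity and suspected causality, the mix of events is distorted as well as the count, and this affects the serious and treatment-related tables most directly.

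A related question touches the primary safety tables. SAP 6.1.1 defines the death row as "adverse event leading to death (as recorded on the AE eCRF page, Did the AE result in Death = Yes", together with Grade 5 AEs, and it defines SAEs from the same page. Yet the VOC page has its own outcome item: "Outcome (recovered without sequelae, resolved with sequelae, ongoing, unknown, death". The SAP does not say how a VOC-page record with outcome death reaches the death row or the deaths listing.

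**Working it through.** The plan gives no figure for this endpoint, so there is none to reproduce. The check is a cross-tabulation, followed by an illustration.

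**Step 1. SAP 3.2.3 terms against protocol 9.4.12.1 and 9.4.12.1.1.**

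| SAP term | VOC-page diagnosis | Match | Default page |
|---|---|---|---|
| Sickle cell anemia with crisis | Uncomplicated VOC | by meaning | VOC |
| Acute chest syndrome | same | by name | VOC |
| Hepatic sequestration | same | by name | VOC |
| Splenic sequestration | same | by name | VOC |
| Priapism | same, if facility visit | by name | VOC |
| Dactylitis | same | by name | VOC |
| Pneumonia | none | – | AE |
| Osteonecrosis | none | – | AE |
| Stroke | none | – | AE |
| Leg ulcers | none | – | AE |

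Five matches by name plus one by meaning make 6 of 10. The first mapping is an inference; neither document states it.

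**Step 2. What SAP 6.2.1 supplies.** It reports total, uncomplicated and complicated VOCs, counts by complicated type, the number of participants with any VOC, VOCs per participant, and a listing. It does not give participants by type, seriousness or death. Dactylitis is missing from its type list, although SAP 3.2.1 counts it as a complicated VOC. Its period is on treatment, with participant-years ending at EOT, whereas the TEAE window in SAP 3.1.1 runs to last dose plus 56 days.

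**Step 3. Illustration on assumed inputs.** Neither document gives a VOC rate, a rate for the other four terms, or the share of VOC-type events that reach the AE page. Let L be VOC-type events per participant-year, q the one-year incidence of the other four terms, and e the share of VOC-type events on the AE page. With one year on treatment and independence of the two groups of terms:

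- Poisson: P = 1 − (1 − q) × exp(−L × e)
- Negative binomial, dispersion 1: P = 1 − (1 − q) / (1 + L × e)

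Setting e = 1 counts every event. For L = 1, q = 0.10, e = 0.10:

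- Poisson, AE page: 1 − 0.90 × exp(−0.10) = 0.186; all events: 1 − 0.90 × exp(−1) = 0.669
- Negative binomial, AE page: 1 − 0.90/1.10 = 0.182; all events: 1 − 0.90/2 = 0.550

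Participants with an event, Poisson / negative binomial:

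| Counted | L = 0.5, q = 5% | L = 1, q = 10% | L = 3, q = 20% |
|---|---|---|---|
| AE page, e = 0 | 5% / 5% | 10% / 10% | 20% / 20% |
| AE page, e = 10% | 10% / 10% | 19% / 18% | 41% / 38% |
| AE page, e = 25% | 16% / 16% | 30% / 28% | 62% / 54% |
| Both pages | 42% / 37% | 67% / 55% | 96% / 80% |

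The direction is the same in every column. The size depends entirely on the assumptions.

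**The case against.** The protocol keeps expected disease events apart by a declared rule and has them monitored by an independent data monitoring committee. SAP 2.2 words the objective as VOCs and SCD-related complications together, and the VOC rate is its companion endpoint. The VOCs are therefore not lost: SAP 6.2.1 reports them, including how many participants had any. The study has no comparator and tests no hypothesis. This stands, and it limits the consequence to the endpoint as labelled. It does not repair that endpoint, because SAP 3.2.3 lists the six terms by intent and SAP 6.2.1 lacks the breakdown and window that 6.2.3 promises.

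Three stronger readings are tempting, and the documents do not support them.

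- A reader might infer that the six rows will be almost empty. The exceptions, the adjudication return route, and events outside the VOC definition (such as priapism without a facility visit) all feed the AE page, and the illustration gives AE-page totals well above zero. Amendment 4 also revised the VOC guidance when participants were already enrolled. The earlier recording rule is not visible, so some earlier VOCs may sit on the AE page.
- A reader might infer that fatal or hospitalised VOCs vanish and that the safety conclusion is biased in the drug's favour. Unexpectedly severe or possibly related VOCs must be reported as SAEs, and SAP 6.1.1 plans a separate deaths listing with no stated restriction to the AE page. What is shown is an unstated data source, not lost deaths.
- A reader might infer that everything needed is already on the VOC page. Protocol 9.4.12.1.1 lists no seriousness or relatedness item, and it places hospitalisation in one item with other facility visits.

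**Conclusion.** The concern holds as a mismatch between endpoint definition and data source. Followed as written, the plan takes six of ten terms from a page on which they are not recorded by default. The incidence of SCD-related AEs is then understated, and the serious and treatment-related sub-tables are filled by selection. The count of six rests on one inferred mapping; without it, five terms match by name.

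The amount cannot be derived from the documents. Over the assumed range (L from 0.5 to 3 per year, q from 5% to 20%), AE-page incidence is 5% to 20% if no VOC-type event reaches that page and 16% to 62% if a quarter do. Counting both pages gives 42% to 96% (Poisson) or 37% to 80% (negative binomial). These figures are illustrative only. The primary safety tables need a clarification of source; a bias in the primary safety conclusion is not established.

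**What to change.** In SAP 3.2.3 and 6.2.3, define the endpoint from the union of AE-page and VOC-page records. State the mapping of VOC diagnoses to the listed terms, including the one for uncomplicated VOC. Apply the same treatment-emergent window to both sources, count each participant once per term, and de-duplicate events held on both pages.

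Alternatively, restrict the list to pneumonia, osteonecrosis, stroke and leg ulcers, and relabel the endpoint as non-VOC complications. Then add participants by VOC type, including dactylitis, to SAP 6.2.1. This avoids counting VOCs under two secondary endpoints.

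In SAP 6.1.1, add a row for VOC-page events with outcome death, and one for hospitalised VOCs if the eCRF records hospitalisation separately. State that the deaths listing draws on both pages.

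The cost is SAP wording and programming. First confirm which fields the VOC eCRF holds, and whether VOC recording continued after Week 48, since protocol 9.4.12.1.1 describes recording only up to that point in the treatment period.

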### 3.3. Exploratory Endpoints

#### 3.3.1. Change from baseline in adhesion of whole blood to microfluidic channels.

Flow adhesion parameters include:

- result from whole blood flow adhesion on Vascular Cell Adhesion Molecules (VCAM) (cells/mm^2)
- result from whole blood flow adhesion on P-selectin (cells/mm^2)
- result from isolated red blood cell flow adhesion on Vascular Cell Adhesion Molecules (VCAM) (cells/mm^2)
- result from isolated white blood cell flow adhesion on P-selectin (cells/mm^2)

Rules for defining baseline are described in Appendix 1.2.

#### 3.3.2. Change from baseline in RBC sickling from peripheral blood smears.

% sickled cells will be derived from the parameters obtained from the blood smear using the following equation:

$$\frac{\text{total number of sickled cells per slide}}{\text{total number of cells per slide}} \times 100\%$$

Rules for defining baseline are described in Appendix 1.2.

#### 3.3.3. Change from baseline in RBC deformability

RBC deformability is measured by Elongation Index (Elmin, Elmax) and Point of Sickling (PoS)

where,

$El_{max}$  is the maximal elongation index, representing overall deformability under normoxic conditions.

$El_{min}$  is the minimal elongation index, representing overall deformability under hypoxic conditions.

PoS is point of sickling or point on the curve during deoxygenation when sickling begins.

Rules for defining baseline are described in Appendix 1.2.

#### **3.3.4. Change from baseline in erythropoietin levels**

Erythropoietin will be measured in IU/L units. Both raw erythropoietin and natural log-transformed erythropoietin will be summarized.

Rules for defining baseline are described in Appendix 1.2

#### **3.3.5. Patient-Reported Outcome Endpoints**

HRQOL will be assessed via patient-reported outcome endpoints and will be summarized.

Rules for defining baseline (when applicable) are described in Appendix 1.2.

- **PROMIS SF Fatigue 13a**

This questionnaire measures fatigue and consists of 13 questions. Each question is scored from 1-5 (1 = “Not at all” and 5 = “Very much”). After appropriate recoding, positively phrased questions (“I have energy” and “I am able to my usual activities”) are reverse scored (e.g. 5 = “Not at all” and 1 = “Very much”) and the raw total score is calculated by taking the sum of response values for each question. All questions must be answered in order to arrive at the raw total score.

- **PROMIS SF Pain Interference 8a**

This questionnaire measures the pain interference and consists of 8 questions. Each question is scored from 1-5 and a total raw score is calculated by taking the sum of response values for each question. All questions must be answered in order to arrive at the raw total score.

- **PROMIS NRS Pain intensity**

This questionnaire measures pain intensity and consists of a single question. Rating ranges from 0-10.

- **PGI-S of fatigue and PGI-S of pain**

These forms are not reflected in the SOA (Schedule of Assessments) of the protocol. However, these data are collected for participants who completed the same form in the parent study and rolled over to the OLE study.

Both forms have 2 questions each and the questions are based on a 5-point scale. For the purposes of summarization, the following numeric response will be assigned to each response category:

Not present / Not at all	0
Mild / A little bit	1
Moderate / Somewhat	2
Severe / Quite a bit	3
Very Severe / Very much	4

- **PGI-S**

This form is not reflected in the SOA (Schedule of Assessments) of the protocol. However, this data is collected for participants who completed the same form in the parent study and rolled over to the OLE study.

This form measures overall status on a 5-point scale. For the purposes of summarization, the following numeric response will be assigned to each response category:

None	0
Mild	1
Moderate	2
Severe	3
Very Severe	4

- **CGI-S**

The form is based on a 7-point scale. For the purposes of summarization, the following numeric response will be assigned to each response category:

Not assessed	Missing
Normal, Not at all ill	0
Borderline ill	1
Mildly ill	2
Moderately ill	3
Markedly ill	4
Severely ill	5
Among the most extremely ill	6

- **EuroQol EQ-5D-5L**

This form assesses the participant's health at the time of the clinic site visit focusing on categories of mobility, self-care, usual activities, pain/discomfort, anxiety/depression and on how good/bad their health is today.

- The visual analog scale (VAS) records the participant's health status score from 0 (worst health) – 100 (best health).
- The descriptive health questionnaire is comprised of 5 dimensions (mobility, self-care, usual activities, pain/discomfort, anxiety/depression), each having 5 levels (1 = no problems to 5 = extreme problems).
- An index score (based on US crosswalk calculator) is calculated for each participant based on the response across the 5 dimensions.

#### • **WPAI+CIQ:SCD**

WPAI+CIQ:SCD is the work productivity and activity impairment plus classroom impairment questionnaire. This form assesses the effect of SCD on the ability to work, attend classes, and perform regular daily activities.

### **3.3.6. Pharmacokinetic Concentration Data**

Plasma and whole blood PK concentration data will be listed and summarized.

### **3.4. Baseline Variables**

The following baseline variables will be summarized. No baseline variables will be used for statistical modeling.

- Demographics: age (years), sex, race, ethnicity, geographic region (North America, Sub-Saharan Africa).

Some of the following baseline data (unless mentioned otherwise) is not collected in C5351005 EDC and will be programmatically included from the parent study database and corresponding ADaM datasets:

- Baseline characteristics: weight (kg) (see Appendix 1.2), height (cm) and SCD genotype from the parent study.
- SCD history: HU use at parent study screening, L-glutamine use at parent study screening.
- VOC history

VOCs (meeting definition in Section 3.2.1) within 12 months of parent study screening visit will be summarized in the following manner:

- a) Total number of VOCs in the past 12 months prior to parent study screening visit across all participants, total participant years in the past 12 months prior to parent study screening visit, annualized incidence rate of VOC in the past 12 months prior to parent study screening visit.
- b) Number of VOCs in the past 12 months prior to parent study screening visit per participant.
- c) Number of participants experiencing at least one VOC of specified type in the 12 months prior to parent study screening visit.

The 12-month VOC summaries will be based on counting individual events over 365 days prior to parent study informed consent date (screening visit).

- SCD complications history from parent study includes (i) historical SCD complications (including episodes ongoing at parent study screening) and (ii) concurrent SCD complications (episodes ongoing at parent study screening).
- Medical History (coded using MedDRA) from parent study.

